4.13.2. Application of Dressings

4.13.2.1. ciNPT

For the knee randomized to receive ciNPT, a PREVENA RESTOR ARTHRO•FORM™ Dressing will be applied over the closed incision immediately after incision closure and cleansing of the application site. Any surgical drains must be routed under the skin beyond the dressing boundary and function independently from the ciNPT. The dressings should not be lifted or prematurely removed after application for reasons other than those related to the device, such as a malfunction or leak alarm. If the dressing is lifted for any reason, a new dressing must be applied; do not re-adhere the same dressing. For the delivery of negative pressure, a PREVENA PLUS™ 125 Therapy Unit will be attached to the dressing tubing, and ciNPT will be initiated in the operating room. If the dressing leaks and a seal cannot be maintained, replacement of the PREVENA RESTOR ARTHRO•FORM™ Dressing is acceptable and will be documented. In the event that the therapy unit malfunctions at any time during treatment, a replacement unit may be used. The dressing will be applied on Day 0 and changed on post-surgical Day 5-7. When removing the dressing, it should always be removed parallel/in-line with the incision and never across the incision line. After changing the dressing, ciNPT will be reapplied for the remainder of the treatment period until 12-14 days of treatment are completed. Treatment removal is addressed in Section 4.14.1.

4.13.2.2. Standard silver-containing dressings

For the knee randomized to the control arm, a silver-containing dressing will be applied over the closed incision immediately after incision closure and cleansing of the application site. Silver-containing dressings will be applied following the product IFU, and the dressing may be replaced as needed throughout the treatment period according to the IFU. At a minimum, the dressing will be removed and changed at the Day 5-7 visit. After re-application of the silver containing dressing at the Day 5-7 visit, treatment will continue until 12-14 days of treatment are completed. Treatment removal is addressed in Section 4.14.2.

4.14. Treatment Removal

4.14.1. *PREVENA RESTOR ARTHRO•FORM™ Dressing*

All subjects should receive ciNPT on the appropriately randomized knee for a duration of 12-14 days post-surgery. Closed incision negative pressure therapy (ciNPT) will be discontinued no later than 14 days after surgery, and the PREVENA RESTOR ARTHRO•FORM™ Dressing will be removed. The PREVENA RESTOR ARTHRO•FORM™ Dressing should be removed parallel/in-line with the incision and never across the incision line. If a subsequent dressing is required, a gauze dressing may be used.

4.14.2. *Standard silver-containing dressing*

All subjects should receive a standard silver-containing dressing on the appropriately randomized knee for a duration of 12-14 days post-surgery. If a subsequent dressing is required, a gauze dressing may be used.

4.15. Post-Operative Assessments

It is recommended that all post-operative assessments occur during the afternoon (local time), if possible, to control for time-of-day effects on the primary and secondary endpoints. The time of day for each postoperative visit will be recorded. In addition, it is recommended that subjects do not undergo physical therapy activities on the day of follow-up visits before completing assessments in order to achieve more accurate measures of swelling, range of motion, and straight-leg-raise tests. If PT is to occur on the same day of a follow-up visit, it is recommended that it occurs after the visit.

4.15.1. *Surgical Site Complications*

The investigator will examine both legs and both incisions of the subject for any evidence of surgical site complications. SSCs will be assessed in the following categories, and interventions to resolve the SSC will be captured:

- Superficial or Deep Incisional Surgical Site Infection (SSI)
- Full thickness skin dehiscence

- Seroma or hematoma requiring drainage or surgery
- Skin necrosis
- Continued drainage determined by an Investigator's visual inspection of the incision after completion of the study treatment period and removal of the study treatment dressing.
- Other complication that requires intervention
 - Investigator will define type of complication

4.15.2. Scar Cosmesis Assessment

The assessments of scar quality in this study will be performed by the investigator or investigator-designated physician for each knee using the Manchester Scar Scale.³³ This visual analog scale includes clinical assessment of the scar color, contour, texture, and distortion.

4.15.3. Straight Leg Raises

Assessments of active straight leg raising (ASLR), which is used to evaluate pain provocation and the ability to load the quadriceps muscle after TKA, will be performed independently for each leg in this study. While lying flat in a supine position on a firm surface (eg, an exam table), subjects will be asked to raise their leg 20 cm off of the flat surface without any assistance. The ability to perform the straight leg raise will be scored for each leg using a six-point scale previously described by Mens et al: 0 = not difficult at all; 1 = minimally difficult; 2 = somewhat difficult; 3 = fairly difficult; 4 = very difficult; 5 = unable to do.³⁴

4.15.4. Health Economics Assessment

Information related to additional hospital admissions, procedures, emergency room visits and/or follow-up care after the subject's TKA during the study period will be documented at all post-surgery visits, including unscheduled visits. Data to be collected will include:

- Hospital admissions related to either knee since previous study visit (the knee that caused the admission will be documented)
 - If admitted, length of the hospital stay
 - Procedures performed on either knee
 - Medications used to treat the cause of admission (ie, the knee)
- Emergency Department (ED) visits related to either knee since previous visit (specify which knee necessitated ED visit)
 - Procedures performed related to either knee
 - Medications used to treat the cause of admission (ie, the knee)

4.16. Concomitant Medications

Concomitant medications will be collected from the time of treatment application through the end of the study. The medication name, start date, end date, and indication will be reported.

Medications required to be reported include:

- Medications required to treat pre-existing health conditions that are active during the study period
- Diuretics
- Anticoagulants (eg, tranexamic acid, acetylsalicylic acid, anti-thrombotic agents, etc)
- Steroids
- Medications used to treat adverse events
- All medications that are used as prophylactic agent(s)

4.17. Prohibited Procedures and Treatments

Skin closure using any type of plastic closure device (eg, Zipline sutures) is restricted in this study. In addition, re-application of ciNPT using a PREVENA ARTHRO•FORM™

Dressing or any other PREVENA™ Dressing is **prohibited** after the treatment period. For the control arm, silver-containing dressings should be removed no later than 14 after surgery, and re-application of any silver-containing dressing past post-operative Day 14 is **prohibited**.

Subjects who undergo a subsequent surgery involving the initial TKA within the 12 weeks must withdraw from the study prior to the subsequent procedure.

Subjects who are in need of a TKA revision on either knee within the 12 weeks of the original study procedure must withdraw from the study prior to the subsequent procedure.

Cross-over therapy is not permitted during the study. Subjects receiving cross-over therapy after completing the original study treatment on either knee (ie, therapy from the arm in which each knee was not initially treated) must withdraw from the study. The reason for withdrawal will be documented.

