3.6. Safety Endpoint

The Safety Endpoint is the incidence of Adverse Events and Serious Adverse Events, including subsequent emergency department visits or subsequent hospitalizations/interventions for either knee.

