4.4. Subject Withdrawal or Termination

4.4.1. Reasons for Withdrawal or Termination

Subjects may withdraw from participation in the study at any time upon request.

The investigator may choose to terminate the participation of a subject from the study with or without their consent for any of the following reasons:

- Adverse events
- Noncompliance
- For any reason that may, in the opinion of the investigator, negatively affect the safety or well-being of the subject

Subjects with the following surgical outcomes will be withdrawn from the study.

- Subject does not undergo a bilateral TKA procedure
- Subject does not receive a “total” knee replacement for each knee. For example, a partial or uni-compartmental knee replacement is performed on one or both sides
- Subject has a surgical incision that precludes placement of either dressing onto the appropriately randomized knee
- Subject has a TKA resulting in a muscle flap

An investigator must terminate participation of a subject from the study for any of the reasons indicated in section 4.17.

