4.4.2. Handling of Withdrawal or Termination

Every effort should be made to complete assessments required for the primary endpoint and safety endpoints prior to the subject withdrawal.

For subjects who are lost to follow-up, the investigator will make attempts to collect at least the vital status (eg, whether the subject is alive) before formally withdrawing the subject from the study. Prior to considering a subject lost to follow-up, at least two documented attempts should be made to contact the subject through all available routes, and a certified letter should be sent to the permanent address on file.

Once the subject withdraws from the study, both knees will be considered withdrawn. A subject may not withdraw only one knee from the study. No further study evaluations will be performed, and no additional data will be collected. The investigator may retain and continue to use any data collected before withdrawal. The subject will not be replaced.

If for any reason the subject is withdrawn by the investigator from this study, the investigator will inform the subject and the sponsor.

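### Mandatory withdrawal before a re-operation ends data collection on both knees, so the re-operation, its outcome and later safety events are not collected although the safety endpoint calls for them

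*Combined protocol and SAP*

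**What the plan says.** Section 4.17 contains two withdrawal rules. The first reads: "Subjects who undergo a subsequent surgery involving the initial TKA within the 12 weeks must withdraw from the study prior to the subsequent procedure". The second applies the same consequence, that they "must withdraw from the study prior to the subsequent procedure", to "Subjects who are in need of a TKA revision on either knee within the 12 weeks of the original study procedure". Section 4.4.1 leaves no discretion: "An investigator must terminate participation of a subject from the study for any of the reasons indicated in section 4.17".

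Section 4.4.2 sets out what withdrawal means. It covers the whole subject ("Once the subject withdraws from the study, both knees will be considered withdrawn") and ends collection: "No further study evaluations will be performed, and no additional data will be collected". The same section asks sites to try to complete the primary and safety assessments before the subject leaves, and allows data already collected to be used.

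Against this stand the outcomes the protocol wants. The safety endpoint in 3.6 is the incidence of adverse events (AEs) and serious adverse events (SAEs), "including subsequent emergency department visits or subsequent hospitalizations/interventions for either knee". Section 4.15.1 plans to capture interventions that resolve an SSC, and one SSC category is "Seroma or hematoma requiring drainage or surgery". Section 4.15.4 plans to document, at every post-surgery visit, admissions, length of stay and procedures on either knee since the visit before. Section 8.2.5 analyses SSC incidence by Visits 5 and 6.

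**The concern.** The protocol defines a safety outcome and, for a subset of subjects, forbids collecting part of it. That subset is selected by the outcome: follow-up stops because a serious local problem led to surgery on the study joint. The opposite knee, which is the subject's own control, is lost at the same moment.

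The denominators add to this. Section 8.2.1 keeps subjects and knees with missing data in the denominator of percentages. A knee withdrawn for re-operation would stay in the denominator for SSC incidence by Visits 5 and 6, while nothing that happens to it after withdrawal can enter the numerator. For that later period it is in effect counted as free of events, and so is the other knee. Data not collected at the time cannot be restored at the analysis stage.

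**Working it through.** **Step 1. Order of events.** Withdrawal comes before the procedure (4.17), it is compulsory (4.4.1), and collection stops at withdrawal (4.4.2). So the procedure always falls after collection has ended. No section makes an exception for it.

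**Step 2. What is kept and what is lost.**

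| Item | Planned in | Can be recorded before withdrawal? | After withdrawal |
|---|---|---|---|
| Triggering AE or SAE | 7.1.2, 7.4, 7.5 | Yes | Outcome may be unknown |
| SSC that requires surgery | 4.15.1 | Yes, once the requirement is established | Resolving intervention lost |
| Reason for discontinuation | 4.18, 8.2.2, 8.2.7 | Yes | Not applicable |
| The re-operation and its outcome | 3.6, 4.15.1, 4.15.4 | No | Lost |
| Hospital stay | 3.6, 4.15.4 | Only the part before withdrawal | Remainder lost |
| Later AEs, SSCs, admissions and interventions, either knee | 3.6, 4.15.1, 4.15.4, 8.2.5 | No | Lost |

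Section 4.15.4 works by looking back from the next visit. A withdrawn subject has no next visit, so that route closes too.

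**Step 3. A possible exception.** Section 7.7 follows AEs still ongoing at the final visit for up to 30 days. It covers treatment-related AEs only, and 4.4.2 appears to rule it out for withdrawn subjects. At best it is a partial route, and the two sections need reconciling.

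**Step 4. Size.** The only planned count that enters is 52 subjects, each contributing one knee per arm (3.1, 8.3.1). That figure reproduces: difference 13.6 - 8 = 5.6, SD 9.2, two-sided 0.05, 80% power gives 43.35 by the noncentral t, so 44 per arm; 44/0.85 = 51.8, so 52. The sample size is not in question here.

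The documents give no re-operation rate. Assume a 12-week risk p per knee of 1% to 4%.

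- Knees per arm: 52p = 0.52 to 2.08.
- Subjects with at least one event, knees independent: 52[1 - (1 - p)²] = 52 × 0.0199 = 1.03 to 52 × 0.0784 = 4.08.

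As a second look, take a per-subject risk r. The chance that at least one of 52 subjects is affected is 1 - (1 - r)^52:

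| Assumed r | Expected subjects, 52r | Chance of at least one |
|---|---|---|
| 1% | 0.5 | 41% |
| 2% | 1.0 | 65% |
| 5% | 2.6 | 93% |

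**The case against.** The best defence is that little is truly hidden. The event that makes surgery necessary arises before withdrawal. It can be entered as an AE with the action taken (7.4), may be an SAE through hospitalization or required intervention (7.1.2), and an SAE goes to the sponsor within 24 hours of awareness (7.5). An unscheduled visit includes AE, SSC and health economic assessments and an end-of-study record (5.2.8). Discontinuations are tabulated by reason and, for AEs, by coded term (8.2.2), and AEs and SAEs leading to discontinuation are reported (8.2.7). Those tables count subjects with at least one event, and no stand-alone re-operation table is specified. The trial is also a pilot of a cleared, marketed device with descriptive safety summaries.

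Much of this stands, and it rules out several stronger readings that a reader might infer:

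- That re-operations leave no trace, or that the data would show about zero. The need for re-operation can be counted indirectly from the trigger and the discontinuation reason.
- That the SSC category of seroma or hematoma is lost. It turns on what is required, which can be established and scored before withdrawal.
- That all interventions are lost. The two rules reach only surgery involving the initial arthroplasty and revisions. Emergency visits, other admissions, non-surgical interventions and surgery not involving the arthroplasty remain collectable, and 3.6 does not single out surgical interventions.
- That the primary result is compromised. It is measured at Day 5-7, so a later withdrawal does not remove it, and the sample size already allows 15% dropout (about 8 of 52).

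What the defence does not answer is the procedure itself, its outcome and everything afterwards on both knees. A reason for discontinuation is not a record of an intervention. Completing assessments before withdrawal cannot describe an operation that has not happened.

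**Conclusion.** The gap is real but limited. For subjects who need surgery on the study arthroplasty or a revision within 12 weeks, the protocol stops collection before the re-operation. It thereby omits that procedure, its outcome, any stay after withdrawal, and later safety events on either knee, all of which 3.6, 4.15.1 and 4.15.4 call for. The omission depends on the outcome and touches both arms, because both knees leave together.

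About 1 to 4 of 52 subjects would be affected if the risk were 1-4% per knee. That range and the independence of the two knees are assumptions without support in the documents. The contradiction between the sections does not depend on them. The primary endpoint is unaffected by withdrawals after the Day 5-7 visit, and the sample size is unaffected. This is a should-fix: few subjects, but among the more serious local outcomes, and not recoverable later. Nothing here bears on whether or how a re-operation should be managed.

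**What to change.** Reconcile 3.6, 4.4.2, 4.15.4, 4.17 and 7.7 (and the cross-reference in 4.4.1) by separating the end of efficacy evaluation from the end of safety data collection:

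- In 4.17 and 4.4.2, state that a subject who has a re-operation on the study arthroplasty, or a revision, stays in follow-up for AEs, SSCs, hospitalizations and interventions on both knees through Visit 6, unless consent is withdrawn.
- In 3.6 and 4.15.4, state that the re-operation is recorded as a safety-endpoint event, with the knee, hospital stay and outcome.
- In 7.7, say whether the 30-day follow-up of ongoing treatment-related AEs applies to subjects who leave early, in words consistent with 4.4.2.
- In the analysis sections, state that volume, circumference and range-of-motion values for the re-operated knee after the procedure are flagged and left out of the main efficacy model, with a sensitivity analysis that includes them.

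The cost is a protocol amendment plus a small amount of added follow-up and record collection for a few subjects. The visits are already in the schedule, but retrieving operation and hospital records goes beyond them. The documents contain no budget, so it cannot be said that this work is already funded.

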4.18. End of Study

Subjects may withdraw or be discontinued from this study at any time (**Section 4.4.1**).

The investigator may discontinue a subject's study participation if the investigator feels it is in the best interest of the subject.

The following information will be documented at the End of Study:

- Last day of study participation
- Completion status – Did the subject complete the study (Yes/No)?
- Reason for study discontinuation

5. VISIT SCHEDULE AND DESCRIPTION OF STUDY VISITS

5.1. Schedule of Visits

Procedure Description	Visit 1	Visit 2			Visit 3 Mid-Treatment Follow-up	Visit 4 End of Treatment	Visit 5 Midterm Follow-up	Visit 6 Long Term Follow-up	Unscheduled
	Screening	Pre-Op	Intra-Op	Post-Op					
Visit Windows	Day -42 to 0	Day 0	Day 0	Day 1	Day 5-7	Day 12-14	Day 35-49	Day 77-91	
Informed Consent	X								
Inclusion/Exclusion Criteria	X	X ¹							
Demographics and Subject Characteristics	X	X ¹							
Medical and Surgical History	X	X ¹							
Knee Society Knee Score	X				X	X	X	X	X
Lower Limb Volume – Circumference measurements (manual and 3D)		X			X	X	X	X	X
Range of Motion		X			X	X	X	X	X
Pain Assessment		X		X ⁴					X
Laboratory Assessment for Pregnancy		X ²							
Bilateral TKA Procedure			X						
Intra-op exclusion criteria			X						
Randomization			X ³						

Procedure Description	Visit 1	Visit 2			Visit 3 Mid- Treatment Follow-up	Visit 4 End of Treatment	Visit 5 Midterm Follow-up	Visit 6 Long Term Follow-up	Unscheduled
	Screening	Day of Surgery							
		Pre-Op	Intra-Op	Post-Op					
Visit Windows	Day -42 to 0	Day 0	Day 0	Day 1	Day 5-7	Day 12-14	Day 35-49	Day 77-91	
Application of Treatment			X						
Concomitant Medication			X	X	X	X	X	X	X
Adverse Events			X	X	X	X	X	X	X
Removal of Study Treatment					X ⁵	X			
Scar cosmesis assessment					X	X	X	X	X
Straight Leg raises					X	X	X	X	X
Health Economic Assessments					X	X	X	X	X
SSC Assessments					X	X	X	X	X
End of Study								X	X ⁶

¹ If visit 1 and visit 2 occur on different days, assessments will be reviewed and updated if changes have occurred.

² For women of child-bearing potential

³ Upon surgical closure of 1st TKA but before initiating 2nd TKA on the contralateral knee.

⁴ Daily post-op pain collection will start the day following bilateral TKA by ePRO.

⁵ Dressings will be removed, and a new dressing placed after assessments completed.

⁶ If the subject is withdrawn early.

5.2. Description of Study Visits

5.2.1. Screening/ Days -42 to 0

The following procedures and assessments will be performed and documented in the subject's medical records/source notes:

- Informed consent
- Inclusion and exclusion criteria
- Demographics and subject characteristics
- Medical and surgical history
- KSKSS (for each knee)

5.2.2. Day of Surgery/Pre-op/Day 0

The following procedures and assessments will be performed and documented:

- Inclusion and exclusion criteria confirmation immediately prior to randomization
- Demographics and subject characteristics update, if the Screening visit and surgery occur on different days
- Medical and surgical history update, if the Screening visit and surgery occur on different days
- Laboratory assessment for pregnancy
- Lower limb volume (for each leg), before surgery
- Range of Motion (for each knee), before surgery
- Pain assessment

5.2.3. Day of Surgery/Intra-op/Day 0

- Bilateral TKA
- Intraoperative exclusion criteria

- Randomization
- Application of treatment
- Concomitant medications
- AE assessment and serious adverse event (SAE) reporting after randomization

5.2.4. Day of Surgery/Post-op/Day 1

- ePro access granted post-op Day 1 for pain assessments
- Concomitant medications
- AE assessment and serious adverse event (SAE)

5.2.5. Mid-Treatment / Days 5-7

The following procedures and assessments will be performed and documented:

- Dressing change/removal of the dressing
- Lower limb volume (for each knee) by measuring lower limb circumferences
- KSKSS (for each knee)
- Range of Motion (for each knee)
- Scar cosmesis assessment (for each knee)
- Straight leg raises (for each leg)
- SSC assessment (for each knee)
- Concomitant Medications
- AE assessment and SAE reporting
- Health Economics assessments

5.2.6. End of Treatment / Days 12-14

The following procedures and assessments will be performed and documented:

- Removal of Dressing
- Lower limb volume (for each knee) by measuring lower limb circumferences
- KSKSS (for each knee)
- Range of Motion (for each knee)
- Scar cosmesis assessment (for each knee)
- Straight leg raises (for each leg)
- SSC assessment (for each knee)
- Concomitant Medications
- AE assessment and SAE reporting
- Health Economics assessments

